Title:

Efficacy and Safety of Citrate Anticoagulation in CRRT for Patients with Liver Failure/DysfuncTION, the CAUTION trial! A retrospective study on etiology of liver failure and their complications.

Background

Continuous renal replacement therapy (CRRT) is a crucial intervention for managing acute kidney injury (AKI) in critically ill patients. Citrate anticoagulation has become a preferred method in CRRT due to its effect in longer filter longevity and less bleeding compared to unfractionated heparin¹. However, its use in specific patient populations, such as those with liver failure or severe shock, necessitates careful evaluation.

Citrate acts as an anticoagulant by chelating calcium, an essential cofactor in the coagulation cascade, thus preventing clot formation within the extracorporeal circuit². The citrate-calcium complex is then metabolized mainly in the liver, where citrate is converted into bicarbonate, and calcium is released back into the bloodstream. This mechanism provides dual benefits: effective anticoagulation and metabolic alkalization.

Patients with liver failure present unique challenges for citrate anticoagulation. Impaired liver function can lead to the accumulation of citrate, resulting in high anion gap metabolic acidosis and hypocalcemia³. These risks underscore the need for vigilant monitoring and potential adjustment of citrate dosing in this population. The aim of the present study is to explore whether the etiology of liver failure, which can range from alcoholic liver disease to drug-induced liver injury or shock liver, influences the incidence and severity of citrate-related complications.

Methods

Study design

A retrospective cohort study will be conducted to compare the efficacy and safety of citrate anticoagulation in CRRT among patients with liver failure/dysfunction and severe shock.

Objectives

1. **Primary Objective:** To determine if the etiology of liver failure impacts the incidence of citrate-related complications in patients undergoing CRRT.
2. **Secondary Objectives:** To compare the efficacy of citrate anticoagulation in terms of renal recovery, filter lifespan, and patient survival between those with liver failure/dysfunction and severe shock.

Participants

- **Inclusion Criteria:**
 - Critically ill patients diagnosed with AKI requiring CRRT.

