- Documented liver failure or significant liver dysfunction (e.g., elevated liver enzymes, bilirubin levels, or clinical diagnosis of liver failure) and clinical diagnosis of shock (NE of 0.25 μ g/kg/min and or association of second vasopressor).
- Age \geq 18 years.

Data Collection and Analysis

- Data will be collected retrospectively from medical records and CRRT logs.
- Statistical analysis will include descriptive statistics for baseline characteristics and outcomes.
- Comparisons will be made between patients with liver failure/dysfunction of various etiology using appropriate statistical tests (e.g., chi-square test, t-test, Kaplan-Meier analysis for filter lifespan).
- **Baseline Assessment:**
 - Collection of demographic data, medical history, and liver function tests (LFTs).
 - Baseline renal function tests and relevant clinical parameters.
- **Safety Assessment:**
 - **Primary Safety Endpoint:** Incidence of citrate-related metabolic complications (e.g., citrate accumulation).
 - **Secondary Safety Endpoints:**
 - Incidence of electrolyte imbalances (e.g., hypocalcemia).
 - Incidence of adverse events related to anticoagulation.
- **Efficacy Assessment:**
 - **Primary Efficacy Endpoint:** Filter lifespan (time until filter clotting).
 - **Secondary Efficacy Endpoints:**
 - Renal function recovery markers (e.g., free from renal replacement therapy).
 - Mortality

References

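### Does the renal recovery endpoint need a rule for deaths, an assessment time and a denominator in the protocol?

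*Protocol*

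**What the plan says.** The Secondary Objectives in the protocol set out "To compare the efficacy of citrate anticoagulation in terms of renal recovery, filter lifespan, and patient survival", so recovery and survival are listed as separate outcomes. Under Efficacy Assessment in Data Collection and Analysis, the recovery endpoint is one line: "Renal function recovery markers (e.g., free from renal replacement therapy". No other marker is named. Mortality is the next bullet, without a time point, and nothing links the two.

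On data and methods the protocol is brief. It states "Data will be collected retrospectively from medical records and CRRT logs", and comparisons are to be made "using appropriate statistical tests (e.g., chi-square test, t-test, Kaplan-Meier analysis for filter lifespan". Kaplan-Meier is tied to filter lifespan only. The inclusion criteria combine acute kidney injury on CRRT with liver failure or dysfunction and a "clinical diagnosis of shock (NE of 0.25 μ g/kg/min and or association of second vasopressor", so deaths during follow-up are to be expected. The protocol gives no mortality rate, recovery rate, sample size or follow-up horizon.

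**The concern.** Being off renal replacement therapy is not the same as having recovered. Taken on its own, the criterion can be met by a patient who dies after therapy was stopped. Restricted to survivors, it compares groups selected by survival, which the study itself compares and which may differ by etiology. The same patients could then yield different recovery comparisons depending on a rule the protocol does not state. Because the data are retrospective, that rule could in principle be chosen with outcomes in view. At stake is the reading of one secondary objective: a difference in patients alive and off therapy might be diluted, hidden or reversed.

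**Working it through.** The protocol has no figure to reproduce, so every rate below is an assumption used only to show how the readings behave.

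**Model.** Let m be mortality, r the proportion of survivors off therapy, and f the share of deaths counted as therapy-free. The rate over all patients is (1 − m)r + fm. If r and f are the same in both groups, the difference (group 1 minus group 2) is (m2 − m1)(r − f).

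**Equal recovery among survivors.** Take r = 0.60 and mortality 0.50 vs 0.80.

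| Reading | Group 1 | Group 2 | Difference |
|---|---|---|---|
| f = 0 (alive and off therapy) | 0.50 × 0.60 = 30% | 0.20 × 0.60 = 12% | 18 points |
| f = 0.25 | 30% + 12.5% = 42.5% | 12% + 20% = 32% | 10.5 points |
| f = 0.5 | 30% + 25% = 55% | 12% + 40% = 52% | 3 points |
| f = 1 | 30% + 50% = 80% | 12% + 80% = 92% | −12 points |
| Survivors only | 60% | 60% | 0 |

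The choice of rule clearly moves the result. But the 18-point gap is (0.80 − 0.50) × 0.60: it comes wholly from mortality, since survivors recover equally. The survivors-only figure is correct for survivors, and the mortality difference that it leaves out would appear under the mortality endpoint. With a smaller mortality gap, 50% vs 60%, the figures are 30% vs 24% at f = 0 and 55% vs 54% at f = 0.5, a shift from 6 points to 1.

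**Unequal f.** The formula suggests that reversal needs f above r, but only when f is common to both groups. With r = 0.60, mortality 0.50 vs 0.80 and f = 0.2 vs 0.5, the rates are 30% + 10% = 40% and 12% + 40% = 52%, reversed with both f below r. With mortality 0.50 in both groups and the same f values, they are 40% vs 30% + 25% = 55%, a 15-point difference at equal mortality. So the share of deaths occurring off therapy matters as well as mortality.

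**Unequal recovery among survivors.** Two cases pull in opposite directions.

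- Mortality 40% vs 64%, r = 70% vs 50%. Counting all deaths as therapy-free gives 42% + 40% = 82% vs 18% + 64% = 82%, which hides a difference that both other readings show (alive and off therapy 42% vs 18%; survivors 70% vs 50%).
- Mortality 40% vs 60%, r = 50% vs 75%. Alive and off therapy over all patients is 0.60 × 0.50 = 30% vs 0.40 × 0.75 = 30%, while survivors show 50% vs 75%.

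The second case decides much of the question. The definition most people would propose, alive and off therapy with everyone in the denominator, can itself hide a difference in recovery among survivors.

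**Against the text.** The harmful reading, f = 1, would have to be a rule in the protocol to be an error there. The wording offers an example of a marker, under a label that speaks of recovering renal function. It does not say that deaths count as recovered.

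**The case for a change.** The strongest case for a change is that who can count as recovered, and when, is part of the endpoint's definition and not merely a choice of estimator. The single criterion named, taken literally, admits a patient who died off therapy. The population makes death a common competing event, the study compares survival as well, and one sentence would remove the ambiguity.

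Much of this stands as description. The survival condition, time point and denominator are indeed absent, and the recovery comparison would depend on them if mortality, or the share of deaths off therapy, differed between groups. What does not stand is the step from an unwritten detail to a defect. Scoring every death as renal recovery goes against the label under which the example sits, and an analyst would be unlikely to do it. Counting a patient who came off therapy and later died as liberated is a defensible choice, not plainly a mistake. An all-patient rate, a survivors-only rate and a competing-risk analysis answer different questions, and reasonable statisticians differ on which to lead with. The worry about choosing the rule late is a reason to settle it in the analysis plan before the data are examined; it does not show that the protocol has fixed something wrongly.

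**Conclusion.** No change to the protocol follows. The endpoint line is incomplete but not wrong: it gives an open-ended example and leaves vital status, assessment time and denominator to be specified, as a statistical analysis plan commonly does. Only the protocol was available here, so such a plan may already settle the matter.

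The possible effect ranges from nothing to a reversal: on the assumed rates, from 18 points in one direction to 12 in the other. The reversal to −12 points requires every death to be counted as therapy-free; a smaller f can also reverse the order if it differs enough between groups. None of these sizes can be tied to this study, because the protocol gives no rates. The endpoint is secondary, mortality is reported next to it so a reader can see what drives a recovery difference, and the primary objective on citrate-related complications does not depend on it. This conclusion assumes that the analysts state their definition when they report recovery. It would differ if the protocol had explicitly counted deaths as recovery.
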